Supplemental peripheral nerve blocks have been studied extensively for post Cesarean delivery pain and have focused primarily on local infiltration with or without catheters, transversus abdominis plane (TAP) blocks, and ilioinguinal iliohypogastric (IIIH) blocks. These blocks have not shown superiority to ITM for dynamic pain outcomes, but may have a role in supplemental or "rescue" analgesia whenever ITM cannot be given (e.g., general anesthesia for Cesarean delivery; contraindication to ITM). The ultrasound-guided quadratus lumborum block (QLB) is a regional anesthetic technique that has shown some promise in improving pain following Cesarean delivery compared to placebo, though no randomized studies have directly compared it to the current gold standard, multimodal analgesia with ITM. Furthermore, QLB may have advantages over the TAP block in terms of its more superficial location (easier ultrasound visualization thereby theoretically conferring improved safety). In this context, the utility of QLB as part of a multimodal analgesic approach that includes ITM for post Cesarean delivery pain warrants investigation.

Objectives:

The objective of this study is to determine if the QLB adds benefit to a multimodal analgesia regimen that includes ITM for patients after scheduled elective Cesarean delivery.

Study Design:

Setting/Participants:

This study will be limited to patients presenting to Magee Women's Hospital (MWH) for scheduled, elective cesarean delivery under spinal anesthesia. We plan to enroll a total of 60 patients for this study. Inclusion criteria include elective cesarean delivery under spinal anesthesia, singleton pregnancy, American Society of Anesthesiologists (ASA) classification score of 2 or less, and term gestational age of at least 37 weeks. Exclusion criteria include: contraindications to neuraxial blockade; anatomical abnormalities affecting spinal or QLB placement (i.e. scoliosis, conversion to general anesthesia); contraindications or true allergies to morphine, NSAIDs, acetaminophen, other oral opioids, or local anesthetics; presence of chronic pain history or opioid dependence on or off maintenance therapy.

Study Interventions and Measures:

Subjects will be randomized to one of two groups: ITM plus sham (saline) QLB and ITM plus true (bupivacaine) QLB. The primary outcome is pain on movement at 24 hours post-cesarean delivery. Other outcome measures that will be assessed and evaluated include:

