We will determine if the quadratus lumborum block (QLB) provides superior analgesia to patients following cesarean delivery compared to the current standard of care, multi-modal analgesia (i.e., ITM and scheduled post-operative non-opioid oral analgesics, with oral opioid analgesics reserved for breakthrough pain).

We will measure side-effects associated with each strategy: standard of care (ITM + care described above, plus sham QLB with saline), and standard of care plus true QLB.

We will measure and model economic ramifications associated with each strategy, modeling factors including drug costs, procedure costs, costs associated with length of stay and re-admissions.

1.3 Background: Briefly describe previous findings or observations that provide the background leading to this proposal.

The quadratus lumborum block (QLB) is similar to the transversus abdominis plane (TAP) block, but differs slightly in regards to the location where local anesthetic is injected. Because of the more posterior location of the QLB, it theoretically confers greater safety due to enhanced visualization (1). The TAP block has been studied extensively for post-cesarean delivery pain, consistently showing that it is not superior to ITM for post-operative analgesia, but that it may have a role in patients with breakthrough pain despite the use of ITM, or in patients who were unable to receive it (e.g. general anesthesia for cesarean, contraindications to neuraxial morphine). ITM is superior to TAP alone for post-cesarean analgesia, but it is associated with a dose-dependent increased risk for opioid related side effects (2,4,5). In 2015, Blanco et. al. published a study specifically using the QLB for postoperative pain after cesarean delivery (1). In this study, they compared a true QLB to a sham QLB all in patients who did not receive ITM, and found that the QLB provided improved pain control and decreased the need for post-operative opioids. Another study in 2016 demonstrated that the QLB is superior to the TAP block in regards to decreasing post-operative pain following c-section (3). Unfortunately, neither study compared the QLB to ITM (part of the current gold standard for post-cesarean delivery pain, multimodal analgesia).

References
(see supporting documentation)

1.4 Significance: Why is it important that this research be conducted? What gaps in existing information or knowledge is this research intended to fill?

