Post-operative analgesia protocol: patients in all groups will be given 30 mg IV ketorolac scheduled q6hrs x 3 doses (unless contraindications). After ketorolac, they will receive 600 mg PO ibuprofen q6hrs scheduled for mild pain (1-3) x 24 hours, as well as Tylenol 500 mg PO q4hrs scheduled for mild pain (1-3) x 24 hours (total acetaminophen dose not to exceed 3000 mg in 24 hours). For breakthrough pain, patients will have PRN oxycodone 5-10 mg PO q4hrs for moderate (4-6) or severe (7-10) breakthrough pain. If needed, some patients may also receive PRN IV morphine or other parenteral opioid if breakthrough pain is severe despite PRN oral oxycodone or if they are unable to take PO medications. All of these medications and doses are typical, standard post-operative orders commonly used for pain control in patients who have undergone a cesarean delivery.

The outcome measures that will be assessed and evaluated in all three groups include:

- VAS pain scores at rest and with movement (VAS pain score with movement at 24 hours will be the primary outcome)
- Time to first request for PRN oral or parenteral opioid
- Total opioid analgesics required throughout hospital stay
- Presence/absence of sedation, itching, and nausea/vomiting
- Vital signs - respiratory rate (RR), and oxygen saturation (SpO2)
- Signs of local anesthetic toxicity (e.g., perioral numbness, ringing in the ears, or metallic taste in the mouth, other non-specific neurological symptoms) within 4 hours of block (assessed at 15min, 30 min, 45 min, 1 hour and 4 hours by nursing or study personnel)
- Breastfeeding success and quality

The primary outcome will be measured at baseline (entry to post-anesthesia care unit, and immediately after QLB) and at 1 hour, 4 hours, 24 hours, and 48 hours following completion of the QLB. Follow-up will occur in the recovery room and in patient's rooms.

Post-operative scores for pruritus will be rated on a numeric 0-3 scale (0, none; 1, mild; 2, moderate; 3, severe), and nausea will be rated on a numeric 0-3 scale (0, none; 1, mild; 2, moderate; 3, severe or vomiting). Perioral numbness, ringing in ears, or metallic taste in mouth will be rated as either present or absent.

Following the final evaluation at 48 hours, participation in the study will be considered complete.

2.6.1

Will blood samples be obtained as part of this research study?

* No

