3.7 Will pregnant women be knowingly and purposely included in this research study?

* Yes

General Requirements: The Federal Policy **[45 CFR 46, Subpart B]** specify that research involving pregnant women and/or fetuses must also conform to each of the

following criteria. Describe how your study meets each of the following criteria. Describe how your study meets each of the following criteria. [45 CFR 46.204 (l)(3) - Human Subjects!]

3.7.1

Where scientifically appropriate, preclinical studies, including studies on pregnant animals, and clinical studies, including studies on non-pregnant women, have been conducted and provide data for assessing potential risks to pregnant women and fetuses. [45 CFR 46.204 (a)] [Include references]

*

The experimental intervention in this study will be performing a quadratus lumborum block (QLB). This block will be performed at the conclusion of an elective cesarean section, thus at that time the baby will have already been delivered and the mother will no longer technically be pregnant. Furthermore, the risk of withholding intrathecal morphine from some patients will only affect pain control following delivery when the mother is no longer pregnant. There should therefore be no risks to the fetus at all as a result of this study. Any risks to the mother such as the potential for increased pain when not receiving intrathecal morphine and any possible side effects as a result of the QLB will occur after delivery and thus pose no risks to her pregnancy.

3.7.2

The risk to the fetus is caused solely by interventions or procedures that hold out the prospect of direct benefit for the women or the fetus; or, if there is no such prospect of direct benefit, the risk to the fetus is not greater than minimal and the purpose of the research is the development of important biomedical knowledge which cannot be obtained by any other means. [45 CFR 46.204 (b)]

*

For the reasons described above in section 3.7.1, there should be no risks to the fetus as a result of this study.

3.7.3

Any risk is the least possible for achieving the objectives of the research. [45 CFR 46.204 (c)]

*

All efforts are being taken during the design of this study, and will be during implementation, to ensure that any risks associated with this study are minimized as much as possible.

3.7.4

No inducements, monetary or otherwise, will be offered to terminate the pregnancy. [45 CFR 46.204 (h)]

*

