3.8 Does this research study involve neonates of uncertain viability or nonviable neonates?

- * No

[reviewer notes.]

3.9 Fetal Tissues: Does this research involve the use of fetal tissues or organs?

- * No

[reviewer notes-]

--->

3.10

What is the total number of subjects to be studied at this site, including subjects to be screened for eligibility?

Note: The number below is calculated by summing the data entered in question 3.11. Any additions or changes to the values entered in 3.11 will be reflected in 3.10.

* 60

3.11

Identify each of the disease or condition specific subgroups (include healthy volunteers, if applicable) that will be studied.

Click on the "Add" button and specify for each subgroup:

- 1) **how many subjects will undergo research related procedures at this site; and**
- 2) **if applicable, how many subjects will be required to undergo screening procedures (e.g., blood work, EKG, x-rays, etc.) to establish eligibility. Do Not include subjects who will undergo preliminary telephone screening.**

*

Subgroup	Number to undergo research procedures	Number to undergo screening procedures
Control (ITM plus sham View QLB)	26	30
Experimental (ITM plus View b upl'vacai'ne QLB)	26	30

3.12

Provide a statistical justification for the total number of subjects to be enrolled into this research study at the multicenter sites or this site.

* Described below:

The primary outcome is the mean numeric rating scale (NRS) pain scores with activity at 24 hours after completion of the quadratus lumborum block. Previous work comparing dynamic pain outcomes among women undergoing cesarean delivery with and without quadratus lumborum block 1 reported median [IQR] pain scores at 24 hours of 2[0-3] in the intervention group and 4[2-5] in the control group. Mean and standard deviation were estimated from this data using mean=median and $SD = IQR/1.35$. For 2 groups, a total sample of 60 subjects (26 in each group completed) is estimated to achieve 80% power to detect differences among the NRS means versus the alternative of equal means using an F test with a 0.05 significance level. The size of the variation in the means represented by the standard deviation is assumed to be 1.00, with a common standard deviation within a group of 2.22. To account for subject dropout and/or ineligibility, 60 subjects will be screened for randomization into 2 groups, with 30 subjects to be screened for each group.

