STUDY TITLE: *Quadratus Lumborum Block versus Intrathecal Morphine for Postoperative Pain Control after Cesarean Delivery*

Principal Investigator: [name]

Source of Support: UPMC Department of Anesthesiology and Perioperative Medicine

NCT: 03261193

Date of Approval: 08/14/2017

STATISTICAL ANALYSIS PLAN

The primary outcome is the mean numeric rating scale (CRS) pain scores with activity 24-hours after completion of the quadratus lumborum block. Previous work comparing dynamic pain outcomes among women undergoing cesarean delivery with and without quadratus lumborum block 1 reported median (IQR) pain scores at 24-hours of 2 (0-3) in the intervention group and 4 (2-5) in the control group. Mean and standard deviation were estimated from this data using mean=median and $SD = IQR/1.352$. For 2 groups, a total sample of 60 subjects (~26 in each group completed) is estimated to achieve 80% power to detect differences among the NRS means versus the alternative of equal means using an F-test with a 0.05 significance level. The size of variation in the means represented by the standard deviation is assumed to be 1.00, with a common standard deviation within a group of 2.22. To account for subject dropout and/or ineligibility, 60 subjects will be screened for randomization into 2 groups, with 30 subjects to be screened for each group.

References:

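### The stated 80% power does not follow from the plan's own inputs (26 per group gives 89%), and neither 3.12 nor the SAP says that the effect and SD come from women without ITM

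*Protocol*

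**What the plan says.** Protocol 3.12 states that "a total sample of 60 subjects (26 in each group completed) is estimated to achieve 80% power to detect differences among the NRS means". The SAP has the same sentence with an approximate sign: "a total sample of 60 subjects (~26 in each group completed) is estimated to achieve 80% power". Both name a two-group F test at a 0.05 significance level.

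The effect and the variability come from one published trial, reference 1 in both places, which reported "median [IQR] pain scores at 24 hours of 2[0-3] in the intervention group and 4[2-5] in the control group". The plan takes each median as a mean and divides the IQR by 1.35 to get an SD. The SD of the group means "is assumed to be 1.00, with a common standard deviation within a group of 2.22".

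Both texts describe that source only as a comparison with and without the block. Protocol 1.3 adds that "they compared a true QLB to a sham QLB all in patients who did not receive ITM". In the present trial both arms receive ITM: "Subjects will be randomized to one of two groups: ITM plus sham (saline) QLB and ITM plus true (bupivacaine) QLB".

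**The concern.** The sample-size paragraph is the only justification given for N. All of its inputs are printed and they agree with one another, so a reader should be able to reproduce the 80%, and cannot. Either an input is missing or the figure belongs to another calculation.

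The second point concerns a design assumption and is not an arithmetic error. The trial asks what the block adds to a regimen that already contains ITM, but it is sized on an effect seen without ITM. Someone reading only 3.12 or only the SAP cannot see this. It matters because the margin over 80% power is modest: it is used up once the true difference drops from 2.0 to 1.76 points, or the SD rises from 2.22 to 2.52.

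**Working it through.** **Inputs** (Protocol 3.12 and SAP)

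- Means 2 and 4, so the difference is 4 − 2 = 2.0 points.
- SD of the means, dividing by the number of groups: √[((2 − 3)² + (4 − 3)²)/2] = 1.00, as printed.
- Within-group SD: both IQRs are 3 wide, and 3/1.35 = 2.22, as printed.
- Alpha 0.05. For two groups the F test is the same as the two-tailed t-test named for the primary outcome in Protocol 2.18.
- 26 completers per group out of 30 screened; 1 − 52/60 = 13.3% allowed for loss.

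The inputs are therefore consistent with one another.

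**Trying to reproduce the 80%**

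- Standard error of the difference: 2.22 × √(2/26) = 0.616.
- Noncentrality: 2.0/0.616 = 3.25. The F-test form is 52 × (1.00/2.22)² = 10.55, which is 3.25².
- With 50 degrees of freedom the two-sided critical value is 2.009. Power from the noncentral t, and identically from the noncentral F, is **89.0%**.

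| Completers per group | Power for 2.0 points, SD 2.22 |
|---|---|
| 20 | 79.3% |
| 21 | 81.3% |
| 26 | 89.0% |
| 30 | 92.9% |

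So 80% power needs 21 per group. Solving for 80% at 26 per group gives a difference of 1.76 points at SD 2.22, or an SD of 2.52 at 2.0 points.

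**Other readings, 26 per group**

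| Reading | Power |
|---|---|
| Normal approximation | 90.1% |
| One-sided t-test | 94.0% |
| 1.00 taken as a sample SD of two means (difference 1.41) | 61.5% |
| Mann-Whitney, relative efficiency 0.864 to 0.955 | 83.9% to 87.5% |
| Alpha 0.025 | 82.2% |
| Alpha 0.0167 | 77.7% |
| Three groups, SD of means 1.00 (dividing by the number of groups) | 94.7% |
| Three groups, means 2, 3, 4 | 82.1% |

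The nearest to 80% are alpha 0.025 (80.5% at 25 per group) and three groups with means 2, 3 and 4 (80.4% at 25). The first changes the stated alpha; the second changes the stated number of groups.

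**Possible origin (inference only).** Protocol 2.6 and 2.17 still say "The outcome measures that will be assessed and evaluated in all three groups include", and 3.7.1 still says that "the risk of withholding intrathecal morphine from some patients will only affect pain control following delivery". Both suggest an earlier three-group design. Means of 2, 3 and 4 have a sample SD of exactly 1.00, but the middle value is an assumption that the documents do not give.

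**If the effect or SD differs under ITM.** The documents give neither figure for women with ITM, so the ranges below are assumptions. All are for 26 per group.

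| Assumed SD | Power for 2.0 points | Difference detectable with 80% power | Expected 95% CI half-width |
|---|---|---|---|
| 2.0 | 94% | 1.59 | 1.11 |
| 2.22 | 89% | 1.76 | 1.24 |
| 2.5 | 81% | 1.98 | 1.39 |

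Holding the SD at 2.22, power is 67% for a 1.5-point difference and 36% for 1.0 point.

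**The case against.** The strongest reply is that the error harms nobody. On the plan's own inputs the trial exceeds its 80% target, N is unaffected, and the SAP marks the 26 as approximate. That is right as far as N goes. It does not rescue the figure: an approximate 26 does not cover a gap from 21, and the statement remains unreproducible in both documents.

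A second reply is that the source population is already disclosed. A protocol reader can follow reference 1 back to section 1.3. This is fair for the protocol, where the information is one cross-reference away. The SAP, read alone, gives no hint of it.

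A third is that printing 89% could itself overstate power. Protocol 2.18 mentions a Bonferroni correction without giving the number of comparisons or exempting the primary outcome, and the means and SD are rough conversions from medians and IQRs. This stands as a condition: the 89% holds at an unadjusted two-sided 0.05, which is the alpha in 3.12, and on the plan's own conversions.

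Finally, the three-group explanation is not unique, because alpha 0.025 fits about as well. That also stands. The explanation is only a lead for the sponsor to check, and the arithmetic finding does not depend on it.

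**Conclusion.** The concern holds. The plan's inputs give 89% power at 26 completers per group, so the stated 80% is 9 points too low for the plan's own effect. The error is in the safe direction and does not call for a different N. The result rests on the difference of 2.0, SD of 2.22 and two-sided alpha of 0.05 printed in 3.12 and the SAP.

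The missing statement about ITM is a gap in disclosure where N is justified. It does not show that the trial is underpowered, because no effect or SD under ITM is available. It does mean that the 89% applies to an effect borrowed from a different comparison, and that power falls below 80% if the true difference is under 1.76 points at the assumed SD. The correction should be made, but it does not threaten the trial's validity.

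**What to change.** Keep N. Ask the sponsor to confirm where the 80% came from, including whether it was carried over from a three-group design or reflects an adjusted alpha. If no unstated input emerges, replace the power sentence in Protocol 3.12 and the SAP with wording such as:

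> With 26 completers per group, power is 89% for a difference of 2.0 points and 80% for 1.76 points (SD 2.22, two-sided alpha 0.05). The 2.0-point effect and the SD were taken from a trial in women who did not receive ITM; power is lower if the effect of QLB added to ITM is smaller.

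Optionally add the illustrative power at 1.5 and 1.0 points (67% and 36%), labelled as assuming SD 2.22. If the sponsor intends the Bonferroni correction to cover the primary outcome, the power should be given at that adjusted alpha instead.

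The cost is a few sentences in two documents and one check of the figure's origin. It needs no extra patients and no change to the analysis.

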- Time to first request for PRN oral or parenteral opioid
- Total opioid analgesics required throughout hospital stay
- Presence/absence of sedation, itching, and nausea/vomiting
- Vital signs - respiratory rate (RR), and oxygen saturation (SpO₂)
- Signs of local anesthetic toxicity (e.g., perioral numbness, ringing in the ears, or metallic taste in the mouth, other non-specific neurological symptoms) within 4 hours of block (assessed at 15min, 30 min, 45 min, 1 hour and 4 hours by nursing or study personnel)
- Breastfeeding success and quality

The primary outcome will be measured at baseline (entry to post-anesthesia care unit, and immediately after QLB) and at 1 hour, 4 hours, 24 hours, and 48 hours following completion of the QLB. Follow-up will occur in the recovery room and in patient's rooms.

2.18 Describe the statistical approaches that will be used to analyze the study data.

* Addressed below:

The primary outcome is the mean numeric rating scale (NRS) pain scores with activity at 24 hours after completion of the quadratus lumborum block. The primary outcome will be compared between groups using the two-tailed unpaired Student t-test. Interval and ordinal data will be compared between groups using the two-tailed Student's t-test or the Mann-Whitney U-test after testing for normal distribution. Categorical data will be compared using a Chi-Square statistic or the Fisher's exact test.

We will apply Bonferroni correction for multiple comparisons. The time-to-first-supplemental opioid analgesic request will be compared by Cox proportional hazard modeling. Subjects who do not request additional analgesia will be censored at the time of delivery. $P < 0.05$ will be used to reject the null hypothesis.

[reviewer notes-]

2.19

Will this research be conducted in (a) a foreign country and/or (b) at a site (e.g., Navajo Nation) where the cultural background of the subject population differs substantially from that of Pittsburgh and its surrounding communities?

* No

Note that copies of training records, licenses, certificates should be maintained in the study regulatory binder and are subject to audit by the Research Conduct and Compliance Office (RCCO).

In addition, individuals planning to conduct human subject research outside the United States must complete an optional module on the CITI training website: International Studies. [Click here](#) to access the instruction sheet for accessing optional CITI modules.

[reviewer notes-]

2.21

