
[reviewer notes-]**3.13 Inclusion Criteria: List the specific criteria for inclusion of potential subjects.**

Elective cesarean planned under spinal anesthesia
Singleton pregnancy
American Society of Anesthesiologists (ASA) classification score of 2 (or less)
Gestational age of at least 37 weeks
Intention to breastfeed infant

3.14 Exclusion Criteria: List the specific criteria for exclusion of potential subjects from participation.

Contraindications to neuraxial blockade (such as clinically relevant coagulopathy, recent anticoagulant use, patient refusal, or localized skin infection overlying the site of needle entry)

Anatomical abnormalities contraindicating spinal or QLB placement

Received/Conversion to general anesthesia

Received supplemental parenteral anesthesia (sedation) for any reason (e.g. unanticipated prolonged surgical procedure)

History of chronic pain

History of chronic opioid use/abuse

History of Subutex, methadone, other maintenance therapy

3.15

Will HIV serostatus be evaluated specifically for the purpose of participation in this research study?

* No

If **Yes**, provide a justification:

[\[reviewer notes-\]](#)

4.1 Select all recruitment methods to be used to identify potential subjects:
Other Strategies: Described below

4.2 **Provide a detailed description of your recruitment methods, including identifying and initiating contact with participants:**

All subjects approached for enrollment into this study are patients being seen by investigators during the course of normal clinical care. Screening of potential patients will occur by obstetrical OR schedule. After review, potential patients will have telephone contact with subjects 2-3 days prior to the scheduled elective surgery.

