
4.14

Will you inform research subjects about the outcome of this research study following its completion?

* No

If Yes, describe the process to inform subjects of the results:

[reviewer notes-]

5.1

Describe potential risks (physical, psychological, social, legal, economic or other) associated with screening procedures, research interventions/interactions, and follow-up/monitoring procedures performed specifically for this study:

*

View	Research Activity: Access to PHI
	Common Risks: No Value Entered
	Infrequent Risks: Breach of confidentiality
	Other Risks: No Value Entered
	Research Activity: Bupivacaine
	Common Risks: No Value Entered
	Infrequent Risks: No Value Entered
	Other Risks: Maternal: Restlessness, anxiety, dizziness, tinnitus, blurred vision, or tremors, depression of the myocardium, decreased cardiac output, heartblock, hypotension, bradycardia, ventricular arrhythmias, allergic type reactions. Newborn: Infant lethargy after breastfeeding.
	Research Activity: Follow-up: Pain and Breastfeeding Questions
	Common Risks: Inconvenience
	Infrequent Risks: Loss of confidentiality
	Other Risks: frustration or embarrassment (if breastfeeding is unsuccessful).
	Research Activity: Research intervention -quadratus lumborum block
	Common Risks: No Value Entered
	Infrequent Risks: bleeding, infection, damage to surrounding structures
	Other Risks: No Value Entered
	Research Activity: Screening procedures
	Common Risks: No Value Entered
	Infrequent Risks: Loss of confidentiality
	Other Risks: No Value Entered

5.1.1

Describe the steps that will be taken to prevent or to minimize the severity of the potential risks:

The quadratus lumborum block (QLB) will be performed by anesthesiology physicians trained in the procedure in the OR in a sterile fashion (sterile prep, sterile gloves, sterile field) to minimize any risk of infection. It will be performed under ultrasound guidance to minimize the risk of any damage to surrounding structures or bleeding. A low concentration of local anesthetic has been chosen for the block, and the total amount administered will be within the known safe total dosage.

To minimize the risks of loss of confidentiality, any data collected by any interactions with participants for the purpose of this research will be stored on departmental computers (password protected, secure servers) or in locked cabinets in faculty offices. Data will be

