All patients participating in this study have the potential to receive direct benefit in the form of possible improved pain control following the procedure. Improved pain control can also lead to other direct benefits such as having an easier time breastfeeding, being better able to bond with and care for their newborn earlier, and potentially being ready for discharge from the hospital sooner.

5.13 Describe the data and safety monitoring plan associated with this study. If the research study involves multiple sites, the plan must address both a local and central review process.

The incidence of any adverse events including any potential complications related to the quadratus lumborum block or inadequate post-operative pain control in any study group will be monitored and documented daily. Any adverse events will be immediately reported to the PI. Any serious adverse event resulting from this study (which are extremely unlikely) would be immediately reported by the PI to the IRB and appropriate action taken. All collected data will be de-identified and stored on departmental computers on secure servers and accessible only by the PI. The PI will have full oversight of the data and safety monitoring plan (DSMP), and will participate along with the other listed co-investigators in the local data safety monitoring. The DSMP will include monitoring for breach of confidentiality, deviations, data safety, changes to risk / benefit ratio, progress of the study, recruitment and retention, timeliness and quality of the data, AEs, UAPs, and subject withdrawals. The monitoring will occur continually during the study with each enrollment of a new subject, and is being completed to maintain the safety of all participants. All Data and Safety Monitoring meeting reports will be submitted to the IRB at the time of study renewal.

[reviewer notes-]

Section 5 - Potential Risks and Benefits of Study Participation

5.14

What precautions will be used to ensure subject privacy is respected? (e.g. the research intervention will be conducted in a private room; the collection of sensitive information about subjects is limited to the amount necessary to achieve the aims of the research, so that no unneeded sensitive information is being collected, drapes or other barriers will be used for subjects who are required to disrobe)

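### Infant lethargy after breastfeeding is a named bupivacaine risk, but no infant safety observation is prespecified, so it would be captured only incidentally and not compared systematically between arms

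*Protocol*

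**What the plan says.** Under bupivacaine, protocol section 5.1 gives one risk to the infant: "Newborn: Infant lethargy after breastfeeding". It gives no frequency. Section 3.13 has "Intention to breastfeed infant" as an inclusion criterion. Section 1.2 says that side-effects of both strategies will be measured.

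The outcome lists in CS2.1, 2.6 and 2.17 cover pain, opioid use, sedation, itching, nausea and vomiting, vital signs and toxicity symptoms. One entry concerns feeding: "Breastfeeding success and quality". It has no instrument, assessor or time point of its own. Toxicity monitoring is specific by comparison: "Signs of local anesthetic toxicity (e.g., perioral numbness, ringing in the ears, or metallic taste in the mouth, other non-specific neurological symptoms) within 4 hours". These signs are checked at five set times by nursing or study personnel.

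Three other places bear on the point:

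- Section 5.1 shows that feeding is asked about after the block: "Research Activity: Follow-up: Pain and Breastfeeding Questions".
- Section 5.13 provides for daily monitoring and documentation of "The incidence of any adverse events including any potential complications related to the quadratus lumborum block", and of inadequate pain control. It does not mention the newborn.
- Section 2.6 ends observation at two days: "Following the final evaluation at 48 hours, participation in the study will be considered complete".

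The SAP covers the primary outcome and the sample size only.

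**The concern.** The protocol identifies a harm to the newborn, selects mothers whose infants are likely to be exposed to it, and sets out to measure side-effects. It then names no measurement for that harm. Section 5.12 lists easier breastfeeding among the possible direct benefits, so the plan looks for the favourable effect on feeding without a defined look at the unfavourable one.

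What is at stake is the quality of the safety information. Spontaneous reports depend on who notices and who thinks to mention it. They give no assurance that every infant was asked about in the same way, so the number of events and the number of infants assessed are not defined in either arm. An isolated report in the bupivacaine arm would have no sham-arm rate to set against it.

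**Working it through.** The plan gives no figure on this point, so there is none to reproduce. The check has two parts.

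**1. The two risks side by side**

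| | Maternal local anesthetic toxicity | Newborn lethargy after feeding |
|---|---|---|
| Named as a bupivacaine risk (5.1) | Yes (e.g. dizziness, tinnitus) | Yes |
| Item in 2.6 and 2.17 | Yes | None |
| Times | 15, 30 and 45 min, 1 h, 4 h | None |
| Assessor | Nursing or study personnel | None |
| Recorded as | Present or absent for the three listed symptoms (2.6) | Not defined |
| General safeguard | Adverse event monitoring (5.13) | The same, newborn not named |

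Two routes remain for the newborn. One is an adverse event report under 5.13. The other is the breastfeeding outcome, which would reflect poor feeding without recording whether the infant was lethargic. Neither prespecifies that each infant is assessed for lethargy.

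**2. What a recorded item could show**

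Inputs: n = 26 infants in the bupivacaine arm, the number per group in 3.11 and 3.12 (singleton pregnancies, 3.13). This assumes that all 26 are in fact breastfed. The event rates p below are assumptions, because the documents give none.

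One-sided 95% upper bound after zero events: 1 − 0.05^(1/n) = 1 − 0.05^(1/26) = 0.109, or 10.9%.

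Chance of at least one event in the arm: 1 − (1 − p)^26.

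| Assumed true rate p | Chance of at least one event | Chance of none |
|---|---|---|
| 1% | 23.0% | 77.0% |
| 2% | 40.9% | 59.1% |
| 5% | 73.6% | 26.4% |
| 10% | 93.5% | 6.5% |

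For a formal comparison at 26 per arm (Fisher's exact test, two-sided 0.05), power is 2.7% for assumed rates of 2% against 10%, 21.7% for 5% against 20%, and 33.4% for 2% against 20%. The item would therefore support a description by arm with an interval. It would not support a confirmatory test.

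**The case against.** The strongest reply is that 5.13 already covers the risk. It speaks of any adverse events; block complications and poor pain control are examples and set no limit. Events go at once to the principal investigator, the plan also tracks changes in the risk/benefit ratio, and 5.2 expects women to stay at least two days, which spans follow-up. This stands. A reader might infer from the outcome lists that the risk cannot be detected, and the documents do not support that. What remains is that detection would be incidental and not uniform across arms.

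Second, the data collection form and flow chart (2.6, 2.8) are attachments that are not shown, and the form may contain an infant item. This also stands, so the claim is limited to what the visible text prespecifies.

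Third, other risks in 5.1, such as heart block, allergic reaction, bleeding and infection, have no dedicated outcome either. This stands in part: not every named risk needs its own item. But those events occur in the enrolled woman, whom the anesthesia team follows (5.2). The newborn is not among the counted subjects and is not named in the monitoring plan.

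Two further inferences should be resisted:

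- A reader might say that poorer breastfeeding in the bupivacaine arm could not be attributed to the block. With randomization, a sham block and blinding (2.6), a between-arm difference would be attributable to it, subject to chance. Only the mechanism would be unclear.
- A reader might set 5.1 against the statement in 3.7.1 that "There should therefore be no risks to the fetus at all as a result of this study". That answer concerns the fetus, and the block follows delivery. A breastfed newborn is not a fetus, so the two sections do not conflict.

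Finally, the stated hypothesis concerns maternal analgesia, and the documents do not propose to claim infant safety. That limits the weight of the point.

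**Conclusion.** The point holds in a limited form. A newborn risk is named, intention to breastfeed is required and side-effects are to be measured, but the visible documents prespecify no infant safety observation. The risk would be captured only through general adverse event reporting or indirectly through the breastfeeding outcome, and could not be compared systematically between arms.

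The size is modest. No primary result, power figure or planned test changes. Systematic collection in about 26 exposed infants would still leave rates up to about 10.9% unexcluded after zero events, and fewer breastfed infants would widen that bound. The case for acting is that the gap is cheap to close.

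The conclusion rests on two assumptions: that the unseen form holds no such item, and that the newborn is not already understood to fall within 5.13.

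**What to change.** - Add to the follow-up breastfeeding questions one item, infant lethargy or poor arousal at feeds (present/absent), at the existing 4, 24 and 48 hour contacts. Ask it identically in both arms, under the blind.
- List it as a safety outcome in 2.6 and 2.17. Report the number of infants with any positive answer and the number assessed, by arm, with an exact confidence interval.
- State in 5.13 that adverse event monitoring includes the newborn.

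If the data collection form already has such an item, only the changes to 2.6, 2.17 and 5.13 are needed.

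The cost is one question per contact and a short protocol amendment, with no new visit, procedure or staff. The downsides are that the answer is a somewhat subjective maternal or nursing report, which blinding keeps comparable between arms, and that precision will be low, so an absence of events should not be presented as evidence of safety.
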